P1: Significant improvements in gait speed (NPW and WWT conditions) following intervention. We will explore **durability** of C-REM effects on these measures at 6 and 12 months post-intervention.

Secondary prediction: Compared to a health control group, C-REM participants will show:

P 2.1: Improved gait variability and other quantitative gait parameters in NPW & WWT.

P 2.2: Improvements in EF and other mobility related cognitive processes such as speed of processing, attention and divided attention.

Tertiary prediction: Compared to a health control group, C-REM participants will show:

P3: Neuroplasticity will be explored and measured with Functional Near Infrared Spectroscopy (fNIRS), an innovative technology that enables imaging during walking.^{33, 34} We reported that older adults showed increased bilateral prefrontal activation on fNIRS during WWT compared to NPW.¹⁶ We predict that after C-REM, participants will demonstrate neuroplasticity, defined as increased oxygenation levels in mobility related prefrontal regions due to compensatory reallocation or shift in activation patterns during WWT.³⁵⁻³⁷ We will also account for other patterns or neuroplasticity changes.

Significance: Mobility disability is the most prevalent type of disability in older Americans.^{38, 39} The C-REM approach may be an effective, accessible, and low risk method to improve mobility related cognitive functions in vulnerable seniors. Demonstrating mobility gains with C-REM will open new or supplemental treatment options for the majority of U.S. seniors who do not engage in physical exercise due to physical, motivational, or socioeconomic reasons.³⁸ Establishing mobility gains with C-REM in this preliminary randomized clinical trial (RCT) will provide scientific and feasibility support for a future large-scale multicenter RCT to establish and contrast the independent and combined roles of physical and mental exercises to prevent mobility disability.

RESEARCH STRATEGY: SIGNIFICANCE

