- **Cross over design:** Such a design is useful if there are no carryover effects. However, previous studies suggest that the effect of C-REM may be seen more than two years after initial training.^{23, 124}
- **Boosters.** Having booster sessions will increase expenses and interfere with assessing durability. Also, health insurers are unlikely to pay for repeat interventions without clear indications limiting generalizability. However, boosters will be considered in follow-up studies.
- **Dose response.** Training dose was based on MindFit protocols⁸⁸ and our pilot.²⁶ MindFit measures training dosage (*type, time, number*). We will analyze dosing effects on our outcomes. Also see C.11.2.

C.3. Outcomes. Primary outcome is post-intervention change in gait speed (NPW & WWT) and SPPB scores. We extended follow-up to 12 months to explore durability of effects. Secondary is mobility related cognitive processes and other gait variables. The tertiary exploratory outcome is neuroplasticity (fNIRS).

We will assess multiple other mobility and cognitive outcomes (see C.12.2 and 12.5). However, we did not designate all these measures as primary; consistent with CONSORT recommendations for clinical trials.^{125, 126}

C.4. Summary. Study procedures and assessments are summarized in **Table 1** below. Study flow in **Figure 3**.

Table 1. Assessment summary

Procedures/assessments	Days 1-3	Week 1 to 8 (3/week)	Week 9	6 mo	12 mo
Screening/ baseline evaluation (C.12.4)	X				
Safety monitoring (E.8)					
Outcome assessment (C.12)			X	X	X
Intervention (8-weeks)					
Post-intervention assessments (C.12.5)			X	X	X XXXXX

C.5. Recruitment & screening. We will contact a random sample of individuals age 70 and over from Bronx and Westchester population lists using methods implemented in our current studies. We will also post flyers

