Outcomes will be assessed by a research assistant supervised by [name] whom will not participate in other aspects of this RCT. Baseline study assessments done in the first week is limited to **90 minutes over 1 day** to avoid fatigue. Testing time per subject is less than in our ongoing aging studies (~180 min), and was demonstrated to be feasible in our pilot study.²⁶ Telephone assessments are **10 minutes**. Post-intervention assessments conducted at 9 weeks, 6 months, and 12 months will be limited to 90 minutes.

Our group developed or validated many of the primary and secondary outcome measures in this RCT (see resumes and refs^{11, 16, 20, 48, 49, 51, 64, 129, 130, 145-154}). We have over 12 years continuous NIH funding for training and supervising assistants to administer these measures in various elderly populations.

C.12.1. PRIMARY OUTCOME (Mobility): We selected the following three primary outcomes to test the efficacy of the C-REM intervention.

C.12.1.a. Gait speed: Gait speed was recommended to FDA as the preferred outcome for RCTs³⁰ because of its good validity, reliability, sensitivity to change, and predictive validity for multiple adverse outcomes.³⁰ We have reported that gait speed highly correlates with mobility related activities in our community.¹⁵⁵

Method: Research assistants will conduct gait evaluations using a 28-foot computerized mat (20-feet recording surface) with embedded pressure sensors (GAITRite). The mat has 4 feet at each end without sensors to account for initial acceleration and terminal deceleration. Subjects will be asked to walk on the mat at their 'normal walking speed' in a quiet and well-lit room. Monitoring devices will not be attached. Our primary outcome is speed (cm/s). However, multiple gait parameters (see ref¹⁴⁷) will be obtained and available for analyses¹⁴⁷ (P1, P.2.1). Subjects will also be assessed walking the course at their fastest speed.

Reliability: We have reported excellent test-retest reliability of gait speed on GAITRite (Kappa >0.9).^{46, 128} Gait speed correlates highly with complaints of mobility limitations, falls and dementia in our studies.^{128, 134}

Practice effects: Gait speed improved only by <2% when tested twice 8 weeks apart in controls in our pilot study suggesting that longer intervals between gait assessments may help minimize practice effects.

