- We will use **intention to treat (ITT) analysis**, which includes all randomized participants in the groups assigned, regardless of adherence with entry criteria, whether C-REM was received, and subsequent withdrawal or deviation from the protocol.¹⁹⁴ ITT analysis is pragmatic because it admits noncompliance and protocol deviations, and gives an unbiased estimate of the intervention effect. Handling missing data is a major issue in ITT, and is dealt with by imputation or sensitivity analysis.¹⁹⁵⁻¹⁹⁷ The linear mixed effects

model is good in handling missing data due to drop out assuming MAR mechanism.^{193, 198-200} Our statistician, [name], is very experienced in these methods; see C.15.²⁰¹⁻²⁰³

Last observation carried forward is used to deal with missing data, but there are major limitations (see refs^{204, 205} for reviews). Hence, we do not propose to use this method.

- We will utilize closed testing methods, involving step-wise procedures, for addressing multiple comparisons/multiple testing, since they are more powerful than single step methods (e.g. Bonferroni).²⁰⁶
- If sessions attended vary, 'dose' effect will be examined in both groups – discussed in C.11.
- **Mediation analysis** (product of coefficients method²⁰⁷) will be conducted to examine whether depression, psychosocial measures (mood, self-esteem, and self-efficacy) as well as changes in proximal cognitive outcomes (attention and EF) mediates C-REM effects on gait speed in NPW and WWT conditions.
- **Gender:** Almost all observational and intervention studies in aging populations have a female preponderance; reflected in our target recruitment table. This gender distribution has been our experience recruiting over 2000 participants to various aging studies at our center for over 10 years.

While gender differences in EF are reported,^{190, 191} there is insufficient information to assume that there will be gender-based differences in C-REM effects on mobility. Gender explained only a very small portion (2.2%) of the individual variance in EF dependent Card Sorting test in a large NIH toolbox validation study.¹⁹⁰ Repeated training on an EF task (DSST) improved performance on the test; but did not show gender differences.¹⁹² The ACTIVE study reported that adjusting for gender did not change main results in their intervention study.⁶⁵ Hence, we decided against gender-based recruitment.

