Nonetheless, given our sample size we can explore any gender based intervention effects in our study. We shall adjust for gender and conduct gender-stratified analysis.

- **Covariates:** The following pre-specified set of baseline covariates^{21, 25, 191} were selected to determine their influence on the treatment: age, gender, education, chronic illnesses, cognitive test performance, pain, arthritis and cardiac fitness.¹⁷⁸ This method is preferred to adjusting for covariates that are imbalanced between treatment groups using significance testing, because it is possible for a covariate to have a strong confounding effect even if the difference in the average value of that variable between the parallel arms is not significant.¹⁹² We will also monitor any change in these measures over the intervention period and analytically account for their effects by including these measures (baseline levels as well as change) in linear mixed effect models to account for possible confounding.
- Adjusting for performance on baseline **cognitive tests** and stratified analysis by baseline cognitive status in the C-REM group will be done.
- Our **dual-task procedures** have been replicated and validated in many published papers.^{4, 13, 24, 29, 75} We recognize that participants may employ, despite the standardized instructions, different strategies when dual-tasking. In the context of the linear mixed effects models, we will examine whether performance and decline on the cognitive interference task (reciting alternate letters of the alphabet alone and in WWT) was related to dual-task costs observed on the primary walking task and will interpret the results accordingly.

C.14.1.b. Power for primary outcome: The primary hypothesis examines change in gait speed (during NPW and WWT conditions) and SPPB. Improvement in speed is ~10 cm/s after 8-12 week PE interventions.^{41, 46, 79, 80} In contrast, gait speed in the non-intervention controls show minimal improvement,⁷⁹ unchanged,⁴⁶ or declined.^{41, 80} Based on these PE effects and our pilot study,²⁶ we conservatively estimate a 5 cm/s improvement post-C-REM, which is ~50% of the mobility effect in PE trials and less than that achieved in our pilot study (**8 cm/s**). This magnitude of change also corresponds to that recommended as small but clinically meaningful change in gait in aging studies.^{10, 11}

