The sample size (420) provides >80% power to detect clinically meaningful differences at significance level of 0.05. The conservative Bonferroni correction for multiple testing was used in sample size calculations. Based on conservatively estimated SDs of 12 cm/s, 20 cm/s and 1.5 points for NPW, WWT and SPPB, respectively, to detect clinically meaningful differences of 5 cm/s for NPW and 0.5 points for SPPB with 80% power,^{10, 11} and a conservatively estimated 10 cm/s for WWT (16 cm/s WWT speed improvement in our pilot study¹³), at least 169 subjects per group are needed. To take account the projected 20% drop out rate at end of intervention, 210 subjects per group will be enrolled.

5 cm/s is the minimal detectable intervention change that we can study with 80% power, and is not the maximal threshold of change expected after C-REM in this RCT. Any improvement >5 cm/s by C-REM will increase power. For instance, we observed **8 cm/s** improvement in our pilot study²⁶ ('substantial improvement' range^{136, 193}), which will provide us >90% power to test our hypothesis in this RCT.

Durability: Assuming cumulative dropout rates of 25% at 6 months, with n=210 per group, we will have 92%, 99% and 75% power for detecting differences of 5cm/sec, 10 cm/s and 0.5 points in NPW, WWT and SPPB, respectively. At 1 year of follow-up, assuming 30% cumulative dropout, we will have 90%, 98% and 72% power

for detecting differences of 5 cm/sec, 10 cm/s and 0.5 points in NPW, WWT and SPPB, respectively. If the difference in SPPB is substantial (1 point), the power will be more than 95% at both time points. However, given the lower power to reliably estimate SPPB change, we designate the durability examination as an exploratory aim. We will seek additional funding to extend examination of durability.

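### The 169 per group and the follow-up powers do not follow from Bonferroni over three primary outcomes: SPPB has about 74% power on that basis, not 80%, and the secondary detectable differences are also too small

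*Combined protocol and SAP*

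**What the plan says.** - **Number of primary outcomes.** C.3 names three: "Primary outcome is post-intervention change in gait speed (NPW & WWT) and SPPB scores". C.12.1 agrees: "We selected the following three primary outcomes to test the efficacy of the C-REM intervention". So does C.14.1.b: "The primary hypothesis examines change in gait speed (during NPW and WWT conditions) and SPPB". Prediction P1 in the Specific Aims names only two: "Significant improvements in gait speed (NPW and WWT conditions) following intervention".
- **Sizing.** C.14.1.b states a significance level of 0.05 and adds: "The conservative Bonferroni correction for multiple testing was used in sample size calculations". It gives no divisor, per-test level or sidedness. The inputs are SDs of 12 cm/s, 20 cm/s and 1.5 points and differences of 5 cm/s, 10 cm/s and 0.5 points for NPW, WWT and SPPB, with 80% power. The result is that "at least 169 subjects per group are needed", raised to 210 per group for 20% dropout.
- **Durability.** With 25% dropout at 6 months, "we will have 92%, 99% and 75% power for detecting differences of 5cm/sec, 10 cm/s and 0.5 points" for NPW, WWT and SPPB. With 30% dropout at 12 months the figures are 90%, 98% and 72%.
- **Analysis.** C.14.1.a plans something other than Bonferroni: "We will utilize closed testing methods, involving step-wise procedures, for addressing multiple comparisons/multiple testing, since they are more powerful than single step methods". The procedure is not named.
- **Secondary outcomes.** C.14.2.a claims 80% power for differences of 0.29 and 0.30 SD at 6 and 12 months, with the same 25% and 30% dropout from 210 per group. No significance level is given.

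**The concern.** With three primary outcomes, the natural reading of a Bonferroni correction is a per-test level of 0.05/3 = 0.0167. The figure of 169 looks too small for that, because the SPPB difference is only a third of an SD. If so, the statement that 420 gives more than 80% power is not true of SPPB on the basis the plan gives for it. A reader would then take SPPB to be as securely powered as gait speed, and a null SPPB result could be given more weight than it deserves. It also matters that the number of hypotheses sharing the 5% error rate depends on which section is read.

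**Working it through.** **Inputs.** SDs, differences, 80% power and 20/25/30% dropout are from C.14.1.b; 210 per group is from C.9. The tests are taken as two-sided. The document does not say so, but the interim level of 0.003 at half information with 5% overall error (E.8.h) fits a two-sided 0.05 design.

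**Step 1. Try to reproduce 169.** Evaluable n per group = 2 × ((z_α + z_β) × SD/difference)². SPPB has the smallest standardised difference (0.5/1.5 = 0.333), so SD/difference = 3 and n = 18 × (z_α + 0.8416)².

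| Per-test level | z_α | n for SPPB | n using t |
|---|---|---|---|
| two-sided 0.05 | 1.960 | 141.3 | 142.2 |
| two-sided 0.025 | 2.241 | 171.1 | 172.4 |
| two-sided 0.05/3 | 2.394 | 188.4 | 189.9 |
| one-sided 0.05/3 | 2.128 | 158.7 | 159.9 |

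The nearest simple choice is 0.025, a divisor of 2, and it fits only approximately. At two-sided 0.05/3, NPW needs 120.6 and WWT 83.8, so neither drives the size.

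**Step 2. Power at the planned numbers.** Completers per group are 210 × 0.80 = 168 at week 9, 210 × 0.75 = 157.5 at 6 months and 210 × 0.70 = 147 at 12 months. Power in percent from the noncentral t, in the order NPW/WWT/SPPB:

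| Time | Stated | At 0.025 | At 0.05/3 |
|---|---|---|---|
| Week 9 (168) | over 80 | 94.1/99.0/78.9 | 92.0/98.5/74.1 |
| 6 months (157.5) | 92/99/75 | 92.5/98.5/76.0 | 90.1/97.8/70.9 |
| 12 months (147) | 90/98/72 | 90.6/97.9/72.7 | 87.7/96.9/67.4 |

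**Step 3. Solve each stated figure for its per-test level.** Ranges cover the normal and t calculations and, for the powers, rounding.

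- n = 169: 0.026 to 0.027
- SPPB 75% and 72%: 0.022 to 0.025
- NPW 92% and 90%: 0.020 to 0.025
- WWT 99% and 98%: 0.020 or higher (uninformative, as power is near its ceiling)

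None reaches down to 0.0167.

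**Step 4. Effect of step-wise testing.** Holm is used as an example because no procedure is named. It was simulated with 400,000 runs per setting and correlations between outcomes of 0 to 0.7. SPPB power at 168 per group is:

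- all three assumed effects hold: about 86%
- one gait-speed effect null: about 79%
- both null: about 75%

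With all effects true it is about 83% at 6 months and 80% at 12 months. Correlation hardly matters.

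**Step 5. Secondary outcomes.** Detectable difference in SD units = (1.960 + 0.8416) × √(2/n) at two-sided 0.05 and 80% power.

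- 6 months: 2.8016 × √(2/157.5) = 0.316, against 0.29 stated
- 12 months: 2.8016 × √(2/147) = 0.327, against 0.30 stated

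Power at the stated differences is about 73% at both times. Detecting 0.29 and 0.30 SD would take 187 and 175 per group.

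**The case against.** **The planned test is not Bonferroni.** C.14.1.a chooses step-wise testing for its extra power, and C.14.1.b calls its sizing conservative. If all three assumed effects are real, SPPB exceeds 80% at week 9. This stands, and it is why the sample size need not change. But the 169 is presented as a Bonferroni result and should reproduce as one, and the recovery depends on the gait-speed effects being real.

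**The analysis model may be more efficient.** A mixed model with baseline covariates could reduce variance. At 0.05/3, a 10% reduction would bring the SPPB requirement to 188.4 × 0.9 = 169.6, and an 8% reduction would roughly match the follow-up powers. So the stated figures do not prove which divisor was used. However, no such reduction is stated, and the text presents its SDs as the basis of the calculation.

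**Sidedness is unstated.** At one-sided 0.05/3, SPPB would have about 82% power with 168 per group, and at one-sided 0.05 the secondary differences would be 0.280 and 0.290 SD, making the stated ones slightly conservative. Neither reading reproduces the stated 169 or the 0.29/0.30 pair, and E.8.h points to two-sided testing. The conclusions are nonetheless conditional on it.

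**Lower follow-up power for SPPB is already disclosed.** True, and durability is labelled exploratory for that reason. The week-9 claim carries no such caveat.

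**Conclusion.** The concern holds. On the plan's own inputs, with two-sided tests and single-step Bonferroni over three outcomes, SPPB needs 189 to 190 evaluable per group rather than 169. With 168 completers it has about 74% power. Even at 0.025 it has 79%, just under the claim. The follow-up SPPB powers are overstated by about 4 to 5 points against 0.05/3 (71% and 67%, against 75% and 72%). Under Holm, week-9 SPPB power ranges from about 75% to 86% depending on whether the gait-speed effects are real. That a divisor of 2 was used is the simplest reading of the figures, but the document does not confirm it.

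The secondary point is separate and minor: the detectable differences should be about 9% larger, assuming two-sided 0.05.

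NPW and WWT have about 92% and 98% power at week 9 even at 0.05/3, so the gait-speed comparisons are not in doubt.

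**What to change.** Keep 420 and change the text only.

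1. State the primary-outcome list once and align P1 in the Specific Aims with C.3, C.12.1 and C.14.
2. In C.14.1.b, state the Bonferroni divisor and that tests are two-sided. In C.14.1.a, name the closed procedure.
3. If the list stays at three, replace the power figures along these lines: *With 168 evaluable per group, power at two-sided 0.05/3 is about 92%, 98% and 74% for NPW, WWT and SPPB; 80% for SPPB would need 189 to 190 evaluable per group. Under Holm, SPPB power is about 86% if all three effects hold, 79% if one gait-speed effect is null and 75% if both are. At 0.05/3, power is 90/98/71% at 6 months and 88/97/67% at 12 months.* Recompute the Holm figures if another closed procedure is chosen. If a variance reduction from the mixed model was relied on, state it and its source instead.
4. In C.14.2.a, state the significance level and sidedness. At two-sided 0.05, restate the detectable differences as 0.32 and 0.33 SD.

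The cost is slightly less favourable power statements. Sample size, outcomes measured, tests and visits do not change.

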
E. HUMAN SUBJECTS

E.1. Study population:

The characteristics of the subjects, recruitment methods, inclusion and exclusion criteria, and minimum numbers to be studied are described in Section C. The study interviewer will conduct the initial telephone-screening interview. Potential subjects will be invited for further in-person evaluations. Study evaluations, enrollment, and in-person interventions will be done at our research center. The study clinician ([name]/[name]) will diagnose and exclude cases following clinical and neuropsychological testing. The statistician will assign unique study ID to each subject. Research assistants at enrollment will determine eligibility.

General inclusion criteria:

1. Adults aged 70 and older, residing in the community. The age criterion is intended to maximize rates of incident mobility disability.
2. Plan to be in area for next three or more years.

3. Able to speak English at a level sufficient to undergo our cognitive assessment battery.
4. Ambulatory. Subjects are classified as 'non-ambulatory' if they are unable to leave the confines of their home and attend a clinic visit. These include subjects who are bed-bound as a result of severe medical illness or those who require assistive medical devices (respiratory support or ventilators) that cannot be transported or those who cannot complete our gait protocols. **We will not exclude subjects who use walking aids (canes, crutches) for ambulation. Subjects who require walking aids to walk outside but are able to complete our gait protocols without an assistive device or the assistance of another person will not be excluded.** Subjects who become non-ambulatory during follow-up will continue participation in the study via telephone interviews and mailed questionnaires.
5. Gait velocity ≤ 1.0 cm/s.
6. Short Physical Performance Battery score ≤ 9 .

General exclusion criteria (one or more criteria):

1. **Presence of dementia** (Telephone based Memory Impairment Screen score (T-MIS) of <5 , AD8, or dementia diagnosed by study clinician at initial visit). These cut scores and procedures have been validated in our and other aging studies.
2. **Serious chronic or acute illness** such as cancer (late stage, metastatic, or on active treatment), chronic pulmonary disease on ventilator or continuous oxygen therapy or active liver disease. Individuals with recent cardiovascular or cerebrovascular event (MI, PTCA, CABG, or stroke) will not be excluded if they meet above inclusion criteria. *Many of these chronic conditions are very common in older adults. Hence, mere presence of these conditions will not be used to exclude subjects if well controlled or of mild severity and if subjects are able to complete training and mobility tasks.*
3. **Mobility limitations solely due to musculoskeletal limitation or pain** (e.g., severe osteoarthritis) that prevent subjects from completing mobility tests. Prevalence of arthritis is $\sim 60\%$ in the Einstein Aging Study,¹ so mere presence of disease will not be used to exclude subjects if they can complete the mobility tasks.
4. **Any medical condition or chronic medication use** (e.g., neuroleptics) in the judgment of the screening clinician that will compromise safety or affect cognitive functioning or terminal illness with life expectancy less than 12 months.
5. **Progressive, degenerative neurologic disease** (e.g., Parkinson's disease or ALS) diagnosed by study clinician and as per medical history.
6. **Hospitalized** in the past 6 months for severe illness or surgery that specifically affects mobility (e.g., hip or knee replacement) and that prevent subjects from completing mobility tests or plans for surgery affecting mobility in the next 6 months.
7. **Severe auditory or visual loss:** Vision is screened using a Snellen chart by the psychological assistant. Also, the neurologist tests visual fields using confrontation perimetry and near vision using Jaeger test types. Significant loss of vision is defined as corrected vision (using reading glasses) less than 20/400 on the Snellen chart with both eyes and inability to read any test sentence on the Jaeger test card with both eyes. Hearing is initially evaluated as part of the screening telephone interview. Subjects who attend the clinic visit will be excluded only if they are unable to follow questions asked in a loud voice (even with hearing aid in place).
8. **Active psychoses or psychiatric symptoms** (such as agitation) noted during the clinic visit that will prevent completion of study protocols. Past history of these symptoms or presence of psychiatric illness not used as exclusion criteria.
9. **Living in nursing home.**
10. **Participation in intervention trial.** Subjects can participate in other observational studies.

We acknowledge that we cannot control for all possible confounders, and that residual confounding can occur in all clinical trials. However, the randomization process in the clinical trial design will allow for equal allocation of potential confounders and effect modifiers between the two study groups.^{2,3}

E.2. Recruitment: To achieve our study aims aged adults will be recruited from a random sample of the Bronx and Westchester County residents, which is comprised of individuals age 70 and over who are in voter rolls by virtue of having voted in local or national elections in the past two years. We will also post flyers and advertisements at local clinics, stores, community centers and offices. We have had experience using this source to recruit over 1000 participants for various aging studies in the past 10 years including our pilot

intervention study. We will also identify potential participants age 70 and older who are patients at Montefiore through Clinical Looking Glass. The timeline for subject recruitment is shown in Table 3 below. The assumptions made in projecting the number of telephone screening interviews necessary to achieve the aims are based on experience in recruitment for the Einstein Aging Study as well as in our pilot study experience described in section B.5.c.^{1, 4, 5} Once telephone contact is achieved and the interview is complete, we assume that there will be a 20% loss due to lack of interest in the study and failure to meet general eligibility requirements and an additional 10% failure on the cognitive instrument (T-MIS). There is an additional 10% loss in the remaining sample due to failure to meet eligibility requirements. We will explore durability of effects up to 12 months follow-up. Due to study logistics and power considerations, durability will be examined as an exploratory sub-aim till month 57.

Table 3. Timetable and projected subject numbers at baseline and at post-intervention assessments.

Study set up	Year: 1 2 3 4 1 2 3 4 1 2 3 4 1 2 3 4 1 2 3 4												5							
	Quarters:	1	2	3	4	1	2	3	4	1	2	3		1	2	3	4	1	2	3
Screening	x	x	x	x	x	x	x	x	x	x	x	x		x	x	x	x	x	x	x
Intervention, n	26	26	26	26	26	26	26	26	26	26	26	26		26	26	26	28	28	26	
Post-intervention tests, n	21	21	21	21	21	21	21	21	21	21	21	21		21	21	21	23	23	21	
6 month follow-up, n				15	15	15	15	15	15	15	15	15		15	15	15	15	15	15	
12 month follow-up, n				14	14	14	14	14	14	14	14	14		14	14	14	14	14	14	
Data cleaning/analysis																				
Interim analysis (DSMB)																	x (when 210 subjects complete intervention)			
Manuscript preparation																				

E.3. Sources for research material: Research material obtained from human subjects will be the results of clinical and neuropsychological testing obtained from study assessments and telephone interviews. The subject and their primary care physician will be informed of all clinical results that are relevant to patient care.

E.4. Potential risks: Answering health questionnaires and mental state examinations involve minimal psychological, social, or other risks. We do not expect any serious adverse events during these non-invasive tests and training programs of attention and executive function. The C-REM interventions involve mental but no physical effort by the participants. The health education control involves computer based health education. The fNIRS procedures utilize light in visible spectrum and do not pose any risk. Minimal discomfort may be experienced from local forehead pressure. Since there are no significant risks associated with the procedures, this study is justified because useful new scientific knowledge will be obtained.

E.5. Protection against risk: The research staff and investigators will be present during all testing. All questionnaire completion will be done at a slow enough pace so as not to tire individuals. If subjects express physical or mental tiredness or discomfort during any of the assessments or training procedures, the procedure will be terminated immediately. Drs. [name] or [name] will be available onsite or by pager at all times to address any safety concerns or clinical issues during the interventions.

Confidentiality will be preserved by use of ID code numbers for identification. ID and name associations will be password protected in an encrypted master file to which only the PIs and statistician will have access. Randomization procedures were discussed in section C.8. Participant data, including computer data disks, will be kept in a locked room. Identifying information about a subject will not be used during the discussion or presentation of any research data. To ensure confidentiality and anonymity during the study, each subject will be assigned a confidential study number. Access to the subject study identification codes or other information will be restricted to the PIs, co-investigators, and study staff, and upon written request, to the Institutional Review Board or other regulatory agencies, or by written request of the subject, released to others. Paper records will be stored in locked file cabinets in the investigators' offices, and all computers used for data management and analysis will be password-protected and located in secure offices.

Dissemination of information: Results of physical examination, questionnaires, and routine clinical tests as requested will be provided to the subjects, who will be encouraged to share them with their personal physician. Results of experimental procedures will not be reported to the participants or their primary physicians as such findings do not bear direct effects on their health or medical care. Subjects will be advised that the results may be published in a manuscript, but their identities will not be divulged.

This clinical trial will be registered prior to study onset with **ClinicalTrials.gov**, which offers the public up-to-date information for locating federally and privately supported clinical trials for a wide range of diseases and conditions.

E.6. Benefits: Our previous experience, the non-invasive nature of most proposed procedures, the general acceptance by practicing physicians of the procedures to be used, and the close supervision and monitoring of the subjects all minimizes the potential risks. Although there are no benefits to the participant other than careful documentation of current cognitive, mobility and functional abilities, which may be useful in evaluating any future changes, there also are no risks to the participant.

E.7. Importance of the knowledge to be gained: The information that is expected to result from these studies should be of importance for understanding the biology, better diagnosing, and treating mobility disability in the aged. The results expected from this project should improve the treatment of mobility and provide information needed for rehabilitation of mobility disability.

E.8. DATA AND SAFETY MONITORING PLAN.

E.8.a. Introduction: All data collection in this clinical trial will be monitored to assure subject comfort, safety, and confidentiality. The clinical trial protocols, data collection instruments, subject recruitment letters, and consent forms will be reviewed and approved by the **Albert Einstein College of Medicine Committee for Clinical Investigations (AECOM-CCI)**. The AECOM-CCI will also approve the creation and structure of the Data and Safety Monitoring Plan.

E.8.b. Membership:

The Data and Safety Monitoring Board (DSMB) will be appointed in consultation with the responsible program official at NIA and in line with federal and IRB guidelines if the study is funded.

E.8.c. Safety Monitoring:

Prior to beginning data collections, [name] and the DSMB Chair will reconfirm that our site has appropriate safety measures in place. The DSMB will meet with the entire research team to review the study protocols. Particular attention will be paid to outcome definition, study design, procedures for recording and reporting adverse events, and informed consent procedures and documentation.

At the initial meeting, the DSMB may recommend modifications or clarification of the protocol, and it will formulate its operating procedures (e.g., meeting schedule, reports due dates for the study statistician, unblinding policy, and what interim data may be released to the investigators). At the initial meeting the plans for interim monitoring for efficacy and futility will be presented to the DSMB as an aid for monitoring the trial (see E.8.h. below).

We will train competent staff to conduct the interventions and assessments, ensure they understand the nature of the interventions, and understand adverse event reporting requirements. Trained clinical assistants, who will monitor the subject for any adverse events, will perform all assessments. We do not expect any serious adverse events during these non-invasive interventions. The clinical assistant will stop the testing procedures if subjects feel stressed or get embarrassed by their performance, and relay the information immediately to [name], [name], or [name]. At least one investigator will be present onsite during all testing and intervention sessions. In addition Drs. [name] and [name] will be available by pager and cellular telephone at all times to address any safety concerns or clinical issues.

E.8.d. Data Monitoring:

Participant confidentiality will be maintained by assigning each subject a unique study ID upon entry to identify and link subject data. ID and name associations will be password protected in an encrypted master file to which only the data manager and PIs have access. Further protection for confidentiality is assured in that we will avoid telnet or FTP remote access. For added security, database copies will be kept in two separate physical locations in locked, fire-resistant containers. Also see E.5.

E.8.e. Interim meetings:

Both closed and open meetings of the DSMB will be held at six-month intervals. In addition the DSMB will meet more frequently as study progress dictates. The study statistician will prepare databases to be sent to the DSMB statistician for the closed session at least 7 days prior to the meeting. The DSMB statistician will bring reports for the closed session to that meeting. She will collect all copies of these reports at the conclusion of the closed session to ensure that study investigators remain blinded to the interim results.

The open session report will focus on patient accrual and demographics, data completeness, and other study performance measures. Only aggregate data will be presented during the open session (i.e., not segregated by treatment). The closed session report will divide study participants according to coded treatment assignment (C-REM or health education control), comparing participant demographics and baseline characteristics, rates and reasons for treatment discontinuation and loss to follow-up, and rates of serious adverse events. The interim efficacy analysis will be included only in the report for the closed session. In addition to reports prepared by the statistician, the Principal Investigators may prepare a report addressing concerns he anticipates the DSMB will have regarding the conduct of the study.

The interim data reports will include:

- Monthly and cumulative accrual
- Baseline characteristics, overall and by treatment group
- Summary of completeness and quality of data collection forms
- Status of enrolled patients, overall and by treatment group
- Assessments of whether study personnel have followed eligibility criteria and other protocol requirements
- Assessment of participant adherence, overall and by treatment group
- Sample size assumptions
- Outcome rates, overall and by treatment group along with monitoring boundaries for efficacy and futility (if the planned interim look is due)
- Listing of serious adverse events by participant ID number and a table of event-specific cumulative rates, overall and by treatment group
- A summary description of all serious adverse events

Only the closed session report will include the comparisons by treatment group.

E.8.f. Adverse Event Monitoring:

Process: DSMB chair, to be named, will perform data and safety monitoring on an ongoing basis. She/he will not be otherwise involved in assessments or interventions in this clinical trial. The PIs or research staff will see all volunteers. All abnormal findings from the clinical, mobility, and neuropsychological assessments done on Day 1 will be documented on a case report form and reviewed by the DSMB chair. Periodic audits from the AECOM-CCI ensure compliance with confidentiality guidelines and adverse events monitoring.

